C7. Investigative team. The team assembled has expertise in clinical and translational research in PAH and RV failure. This group has collaborated for over five years in the areas of sex hormones, endothelial cell and vesicle biology, and cardiopulmonary function with funding and publications in these areas as well as participation in PAH clinical trials.^{5, 101, 106–109} Collaboration with the NO Metabolomics core at Pittsburgh will greatly enhance measurement of NO end points in human and PAEC samples.

C8. Experimental Plan

[figure not shown]
C8.a. Study design. We propose a “proof-of-concept” crossover study to examine the safety and efficacy of 50 mg daily of DHEA for 18 weeks in patients with World Health Organization (WHO) Group 1 PAH (Figure 9). The primary outcome is RV longitudinal strain. Secondary outcomes include the effects of DHEA on markers of RV remodeling (**Aim 1**) as well as HRQOL, other PAH end points, side effects and safety. We will determine DHEA’s effects *in vivo* in the cross-over trial (**Aim 2**) and *in vitro* on NO and ET-1 pathways in PAECs from subjects with PAH and whether these effects differ by sex (**Aim 3**)

C8.b. Scientific rigor. The selection of the cross-over design by definition eliminates between-subject variability when comparing drug to placebo and allows for a much smaller sample size than would ordinarily be necessary (e.g., in a parallel arm trial) to maintain the same power. Since each subject acts as their own control, it also prevents against the imbalance of

other important factors related to rigor, namely age and race/ethnicity. However, differences in drug effectiveness by age, sex, etc. can still be assessed. This design will also allow us to examine patient-level responses in carefully selected end points (imaging, biomarker, functional, HRQOL) so that we may assess for potential interactions by age and race/ethnicity (as well as sex and PAH sub-type) and time by treatment effects while reducing variability and improving precision.

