Phone call		X	X				X	
Medical history	X							
Medications	X	X	X		X	X		X
History and physical exam	X	X	X		X	X		X
Laboratory/safety								
CBC, Chem 7, hepatic	X	X	X		X	X		as indicated
Hormone levels	X	X	X		X	X		as indicated
Insulin levels	X	X	X		X	X		as indicated
Cholesterol levels	X	X	X		X	X		as indicated
Triglyceride levels	X	X	X		X	X		as indicated
End points								
Aim 1: Cardiac MRI	X		X			X		
Aim 1: NT-proBNP, galectin-3, RAGE, redox	X	X	X		X	X		
Secondary: SF-36v2, emPHasis-10, FC, 6MWD	X	X	X		X	X		
Aim 2: NO-related markers	X	X	X		X	X		
Aim 2: ET-1	X	X	X		X	X		
Study procedures								
Dispense study drug	X							
Medication adherence		X	X		X	X		
Adverse events		X	X	X	X	X	X	X

subjects will be blinded to treatment order allocation. DHEA and placebo will have identical packaging, taste, and smell. Study drug will be dispensed at the start of each treatment phase (weeks 0–18 [Period 1]; 22–40 [Period 2]) with phone calls as outlined.

C8.j. Safety monitoring. The research coordinator ([name] RN, BSN) and research assistant will be available 24/7 by phone as needed for side effects and adverse events. An unscheduled study visit can also be performed if lab abnormalities on safety labs require retesting. Provisions for an unscheduled study visit can be found in Table 6. RIHPHC clinicians and research staff including the study PI will be capable of breaking the blind in case of an adverse event. A data safety monitoring board (DSMB) consisting of three independent clinician scientists with expertise in cardiology, pulmonology and/or endocrinology and a biostatistician with clinical trial experience will be assembled to review enrollment targets, protocol deviations, violations, and adverse events as described below. Conference calls will occur throughout the study period and on an as needed basis for serious adverse events. Please see Section C8.m.6. for specific safety end points and **Data and Safety Monitoring** document for further details.

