C8.k. Drop-out. Subjects may end participation by completion of the trial, loss-to-follow-up, withdrawal of consent, or death. In the last three RCTs conducted at our center ($n = 21$) we have had no patients lost to follow-up (rare in this patient population) and two patients (11%) withdraw. In our power calculations, we have anticipated a 10% drop-out rate; any subjects who need to withdraw from the study will continue study assessments whenever possible and be analyzed in an intent-to-treat fashion.

C8.l. Outcomes for the crossover trial. The primary outcome will be changes in longitudinal strain with DHEA (**Aim 1**). Secondary outcomes will include RVEF, NT-proBNP, galectin-3, RAGE, MPO and sNOX2-dp levels (**Aim 1**), sex hormone levels, HRQOL, WHO functional class, 6MWD, side effects, and safety of DHEA in PAH. We considered using right heart catheterization as a study end point but given the cross-over design (which has benefits in terms of power and precision) this would require three right heart catheterizations which poses undue burden on (and risk to) participants and a threat to feasibility. Additional end points (e.g., HRQOL) were selected based on prior DHEA trials demonstrating efficacy in similar disease states with high relevance to PAH. **Aim 2** outcomes will include changes in NO and ET-1 molecules with DHEA treatment.

C8.l1. Aim 1: Longitudinal strain and RVEF. We have a core MRI facility with a Siemens 1.5T Aera with full Advanced Cardiac Package and XJ Gradients (33 mT/m @ 125 T/m/s) that provides research grade studies at a greatly reduced cost. A single reader ([name], PhD) will be blinded to subject and study visits and will read studies in randomly sequenced batches; 10% of the studies will be re-read by the same reader and 10% of scans will be re-read by a second reader for intra-reader and inter-reader reliability estimates. [name] research focuses on cardiac MRI and he is experienced in RV imaging in PAH. A standardized MRI protocol is proposed:

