C8.o. Analysis plan for the crossover trial. Demographics and clinical data will be provided, stratified by sex as well as PAH subtype. This data will also be tracked for screen failures and drop-outs. Continuous data will be expressed as medians and ranges and categorical data will be expressed as frequency and percentages. Analyses will follow the intention-to-treat paradigm. All end points will be modeled using generalized estimating equations (GEEs), nesting repeated measures within patient and including terms for sex, age, race/ethnicity, PAH-subtype, randomization, and time point, along with all 2-way and 3-way interactions in which carry-over or period effects will be considered. Distribution will be chosen based on inspection of model residuals. Classical sandwich estimation will be used to adjust for model misspecification after maximizing the appropriateness of distribution selected. Orthogonal linear estimates will be constructed within GEEs to test each hypothesis (see Aims) and presented both as the percentage change and absolute change in RV measures (**Aim 1**), changes in NO products and ET-1 (**Aim 2**), and secondary end points. No adjustment for multiple comparisons will be made given the pilot nature of the study. The main effect of DHEA and interactions of DHEA with sex (as well as age, race/ethnicity, PAH-subtype) will be tested within models, with use of visualizations including individual scores for exploratory analysis. Hypotheses will be two-tailed.

C8.p. Sample size and power for the crossover trial. We anticipate a 10% drop-out rate and calculated power based on an anticipated sample size of 24 subjects (12 men, 12 women). As this is a pilot study, detection of a signal (even if not statistically significant) and “proof of concept” that DHEA treatment may improve RV phenotype and alter major PAH regulators would encourage the pursuit of a

larger Phase II parallel arm trial. Time by treatment and PAH subtype by treatment interactions will also be considered as part of 3-way interactions terms in GEE.

C8.p1. Aim 1: Power to detect differences in RV longitudinal strain.

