We will have excellent power to detect clinically relevant changes in RV strain ($\alpha = 0.05$) (Table 7). A $\geq 5\%$ improvement in RV strain (measured by echocardiography; less precise than MRI) occurs with approved PAH therapies and predicts clinical stabilization and survival in PAH.⁵⁶ We have more than enough power to detect this estimate, and effects even as small as 3%. We need this number of patients in order to perform sex-specific analyses (and test for treatment x sex interaction), where we will have 80% power to detect a 4% difference in sex-specific analyses with the presence of an interaction. Power for treatment x PAH subtype interactions will mirror these estimates. We will also have sufficient power to detect changes which approach clinical relevance in RVEF^{61, 139} and NT-proBNP¹⁴⁰ ($\alpha = 0.05$) (Table 8).

C8.p2. Aim 2: Power to detect differences in nitrate and ET-1 levels.

We will have excellent power to detect small ($0.05 \mu\text{M}$) differences in nitrite levels with DHEA treatment based on conservative previously observed estimates ($\alpha = 0.05$).^{25, 141} We will have excellent power to detect small (well-less than 2 pg/mL) differences in ET-1 levels with DHEA treatment ($\alpha = 0.05$). Changes of this magnitude would be consistent with clinically relevant changes in ET-1 with ERAs.¹⁴²

C9. Aim 3: PAEC response to DHEA. In order to minimize burden of the trial participants (and to guarantee more catheter tips), PAECs from men and women undergoing right heart catheterization at the RIHPHC as part of PAH diagnosis or treatment and meeting the same inclusion/exclusion criteria for the cross over trial will be included. As with our preliminary data, these experiments will be performed in our Centers of Biomedical Research Excellence in Stem Cell Biology (PI: [name], P20 GM103468) and Cardiopulmonary Vascular Biology (PI: [name]; Laboratory Core PI: [name], P20 GM103652). We will also examine the effect of DHEA on PAECs obtained from two additional sources: 1) commercially available human PAECs, 2) those obtained from the distal pulmonary circulation of PAH lung explants available through the Pulmonary Hypertension Breakthrough Initiative (PHBI) (PI [name], R24 HL123767; see letter of support).

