constitute a “missed opportunity” to study results of *in vivo* controlled DHEA exposure *in vitro*. We did not incorporate catheterization into the study protocol in an effort to minimize burden but did restrict eligibility for this aim to match inclusion/exclusion criteria for the trial. We perform dedicated right heart catheterizations in 40 – 60 patients yearly, providing ample opportunities to obtain PAECs from PAH patients. Over the last twelve months since this protocol was initiated, PAEC samples have been collected in 57 patients. The PAECs collected (and their response to DHEA exposure) may not represent the phenotype of PAECs from small resistance vessels in PAH (which will also be included for comparison, Section C9). PAH patients have changes in proximal PAs which contribute to circuit compliance and ventricular coupling¹⁴⁷, however, making the proposed experiments relevant. Moreover, recent studies using induced pluripotent stem cells from dermal fibroblasts of PAH patients showed that derived endothelial cells function the same as distal PAECs isolated from explanted lungs.¹⁴⁸ PAECs obtained from lung explants represent end-stage PAH, whereas our method captures PAECs from patients at variable stages of disease. Finally, this is a very novel approach with which we have become increasingly facile in a disease state in which tissue availability is extremely limited.

C13. Summary. This pilot double-blind cross-over trial will test the efficacy and safety of DHEA in men and women with PAH and will characterize the interaction of sex- and sex-hormones with major pathologic drivers of pulmonary vascular and RV dysfunction. Complementary *in vitro* experiments will offer additional insights into mechanisms of sexual dimorphism in PAH. The first study of its kind, we will build a foundation for sex- and hormone-based treatment precision in this rare and progressive disease.

Amendments and Addendums:

Amendment 1 – PAEC Biobanking and RNA Sequencing

Pulmonary arterial cells (PAECs) collected from catheter tips may undergo RNA sequencing as part of an advanced characterization protocol, representing a continuation of the aims of Aim 3 above. The PAECs for RNA Sequencing will be sourced from the current study’s subjects and from a previous biobank (PI: [name], IRB Committee #: 016311). Furthermore, all PAEC cultures will be preserved for future, unknown testing and stored in accordance with the Lifespan HRPP Specimen banking guidelines.

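### Side effects are left to an all-end-point GEE that can break down when events are sparse, and no interval or upper limit for harm is planned

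*Combined protocol and SAP*

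**What the plan says.** Safety is a stated purpose of the trial. C8.a describes a "crossover study to examine the safety and efficacy of 50 mg daily of DHEA for 18 weeks in patients" with PAH, and C13 says the trial "will test the efficacy and safety of DHEA in men and women with PAH". C8.l ends its list of secondary outcomes with "sex hormone levels, HRQOL, WHO functional class, 6MWD, side effects, and safety of DHEA in PAH". C8.j uses the same term, end points, for safety: "Please see Section C8.m.6. for specific safety end points". C8.m6 names the queried effects (skin changes, acne, alopecia, hirsutism) and the safety laboratory tests.

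The only inferential method for the trial is in C8.o: "All end points will be modeled using generalized estimating equations (GEEs), nesting repeated measures within patient". The model includes interactions up to third order, chooses the distribution from the residuals, uses the classical sandwich variance and makes no multiplicity adjustment. The section closes with "Hypotheses will be two-tailed". It names no link function. It also says categorical data will be summarised as frequencies and percentages.

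Neither C8.j, C8.m6, C8.o nor C8.p gives a confidence interval, upper limit or power figure for a safety end point. C8.p1 and C8.p2 cover only RV measures, NT-proBNP, nitrite and ET-1. C8.j provides for DSMB review of adverse events and defers further detail to a Data and Safety Monitoring document that is not part of this file.

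**The concern.** A GEE with a sandwich variance is a reasonable general tool for repeated continuous measures. It suits rare binary events in 24 patients badly, for two reasons.

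First, events may be absent on one treatment. The logit or log-link contrast then has no finite value, and the printed standard error and p value reflect where the software stopped iterating.

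Second, a two-tailed test of difference does not answer the question a safety reader asks, which is how large a harm is still compatible with the data. At this size the answer is quite a large one, and the planned output would not show it. The reader planning the next trial would have percentages and p values but no bound on risk.

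**Working it through.** **Inputs from the documents.** 26 randomised, 10% drop-out, 24 analysed (C8.c, C8.k, C8.p); two-tailed tests (C8.o); alpha 0.05 (stated for the efficacy power figures and carried over here). Check on N: 26 × 0.9 = 23.4, and 24 / 0.9 = 26.7, so 24 agrees with 26 to within rounding. There is no safety power figure to reproduce.

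**Assumptions.** The documents give no side-effect rate. I take 5% and 10% on placebo and count each patient once per treatment condition (event or no event).

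**1. How often one condition is event-free.** With event rate p on both treatments and independence within patient, q = (1 − p)^24 and P(exactly one empty) = 2q(1 − q).
- p = 5%: q = 0.292; 2 × 0.292 × 0.708 = 0.41.
- p = 10%: q = 0.080; 2 × 0.080 × 0.920 = 0.15.

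Within-patient correlation lowers this somewhat. With correlation 0.3, the chance that a patient is event-free on both treatments is (1 − p)² + 0.3p(1 − p), which is 0.917 at 5% and 0.837 at 10%. Then 2(q − 0.917^24) is about 0.34, and 2(q − 0.837^24) is about 0.13.

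**2. What the GEE does then.** Logit GEE with sandwich errors, placebo event-free:
- With 1, 2 and 4 events on DHEA, the treatment coefficient stops at 22 to 24.
- The reported SE ranges from 1.04 to several hundred, or is not computable, depending on the model terms and the software.
- The true maximiser is infinite, so none of these outputs is an estimate.

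The interactions add to this. A single empty sequence-by-period cell makes a model with that interaction diverge. With 12 patients per sequence and a 5% rate, any one such cell is empty with probability 0.95^12 = 0.54.

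**3. Identity scale.** For 4 versus 0 events the risk difference is 4/24 = 0.167. SE = √(0.167 × 0.833 / 24) = 0.076, so z = 2.19 and p = 0.028. The exact paired test gives 2 × 0.5^4 = 0.125. It first reaches 5% at 6 versus 0 (2 × 0.5^6 = 0.031); 5 versus 0 gives 0.0625.

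**4. Power to flag a true excess, n = 24.** Exact enumeration of paired outcomes; ranges cover the exact McNemar, McNemar chi-square and sandwich-type Wald tests, with within-patient correlation 0 to 0.3.

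| True excess | Placebo 5% | Placebo 10% |
|---|---|---|
| +10 points | 4–22% | 5–22% |
| +15 points | 15–46% | 14–40% |
| +20 points | 30–69% | 26–60% |
| +25 points | 47–86% | 40–77% |

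**5. What an interval would show.**
- Zero events in 24: 1 − 0.05^(1/24) = 11.7% (one-sided 95%), or 1 − 0.025^(1/24) = 14.2% (two-sided 95%).
- Upper 95% score limits for the paired difference: 0 versus 0 events, +13.8 points; 2 versus 0 (exact p = 0.50), +25.8 points; 3 versus 0 (exact p = 0.25), +31.0 points.

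**6. Safety labs (paired t, n = 24).** Power is 65% for a shift of 0.5 SD of the paired difference and 80% for 0.6 SD. It is 35% for 0.5 SD within one sex (n = 12). These models remain finite; the only gap is the interval.

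**The case against.** The strongest reply is that the documents never say a non-significant result will be taken as evidence of safety. That is true. A reader might infer such a claim from a plan that says it will test safety, but the text does not support it. C8.p ties the next trial to a signal in RV phenotype and PAH regulators, not to a safety p value. The plan also reports frequencies and has a DSMB, and a monitoring document may say more. All of this stands and limits the point to what C8.o specifies. But neither frequencies nor DSMB review gives an interval, and the monitoring document cannot be assessed here.

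A second reply is that C8.o fixes no link and promises absolute changes, so an identity scale is open to the analyst. This also stands. It would be wrong to say that the model fails in every case where a study period is empty. An identity link stays finite, and if only a calendar period is empty while both treatments have events, the logit treatment effect is finite in a main-effects model. But the choice is left until the data are seen, and step 3 shows the identity version can overstate the evidence.

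A third reply is that low power does not mean that a null result probably conceals harm. Correct: power is the chance of a result given a harm, not the reverse. At +25 points most of the tests considered would detect the excess more often than not. Nor is any general false-alarm rate for the side-effect model supportable, because results at separation depend on software and stopping rules.

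**Conclusion.** The point holds as a gap in C8.o. Sparse binary side effects fall under a model that may have no finite treatment contrast, and no interval or upper limit for harm is planned.

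Under a logit or log link with no drug effect, the chance that exactly one treatment condition is event-free is about 41% at a 5% rate and 15% at 10%, or somewhat less with within-patient correlation. On the identity scale the contrast is finite, but its sandwich p value can be well below the exact one. At a 5% placebo rate, a true excess of up to about 15 points would be missed more often than not, and zero events in 24 excludes only rates above about 12%.

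The event rates are assumptions, because the documents give none. No acceptable-harm margin is needed for the point to stand or to be fixed. It should be corrected, but it does not threaten the primary analysis.

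**What to change.** In C8.o, exempt side effects and adverse events from the all-end-point GEE. For each queried side effect and adverse-event class, report:
- patients affected on DHEA and on placebo;
- the exact one-sided 95% upper limit for the DHEA rate;
- an exact or score paired 95% CI for the within-patient risk difference, with the method named in advance. The choice matters: for 4 versus 0 events the score interval runs from +0.6 to +35.9 points and excludes zero, while the exact test gives p = 0.125.

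For safety labs, keep the model-based DHEA-minus-placebo difference, report its 95% CI and read the limit on the harmful side. Add a sentence that non-significance will not be reported as evidence of safety.

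The cost is a few lines of text and standard calculations, with no new data or patients. The downside is that the safety statement becomes more modest.

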Study end points are subject to measurement error and missingness. Measurement error will be minimized by using validated methods with demonstrated precision in experienced laboratory and imaging cores with QC in place. Every effort will be made to minimize missing data via study procedures, close follow-up, and subject retention efforts. Bias will be minimized by masking patients, investigators, and personal and randomizing the treatment periods. While the proposed sample size is small, the cross-over design by definition optimizes statistical efficiency and minimizes confounding given each participant is their own control and treatment order is randomized. Multiple comparisons could result in Type I error, but our power calculations are based on distinct hypotheses about RV phenotype. Because of the cross-over design, small differences are likely to be detected making Type II error unlikely.

Figure 9. Study protocol

C8.c. Subjects. We will randomize 26 subjects stratified by sex (13 women, 13 men) and PAH type (idiopathic PAH vs. other) from the Rhode Island Hospital Pulmonary Hypertension Center (RIHPHC) to active treatment (Period 1), placebo (Period 2) or to placebo (Period 1), active treatment (Period 2) (**Aims 1, 2**). PAH patients meeting the same inclusion criteria (Table 5) undergoing hemodynamics will be eligible for PAEC collection (**Aim 3**).

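### The uncorrected sandwich variance, with 24 to 26 patients as clusters, does not hold the two-sided 5% level: about 7-9% overall and 9-10% within one sex under the usual normal reference

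*Combined protocol and SAP*

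**What the plan says.** - **Model (C8.o).** "All end points will be modeled using generalized estimating equations (GEEs), nesting repeated measures within patient", "including terms for sex, age, race/ethnicity, PAH-subtype, randomization, and time point, along with all 2-way and 3-way interactions".
- **Variance (C8.o).** "Classical sandwich estimation will be used to adjust for model misspecification after maximizing the appropriateness of distribution selected". No bias correction, t or F reference, degrees of freedom or permutation check appears there or elsewhere in the document.
- **Error level.** C8.o: "Hypotheses will be two-tailed". C8.p1 claims "excellent power to detect clinically relevant changes in RV strain ($\alpha = 0.05".
- **Number of clusters.** C8.c: "We will randomize 26 subjects stratified by sex (13 women, 13 men". C8.p: "calculated power based on an anticipated sample size of 24 subjects (12 men, 12 women".
- **Use within sex (C8.p1).** "We need this number of patients in order to perform sex-specific analyses (and test for treatment x sex interaction".
- **Context.** C8.o makes no multiplicity adjustment because the study is a pilot. C8.p says that a signal short of significance could still support a Phase II trial.

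**The concern.** The sandwich variance is built from squared residuals, and fitted residuals are smaller than true errors. With hundreds of clusters the difference is negligible. With 24 it is not, and with 12 it is larger still. The standard errors are then too small, the tests reject too often, and nominal 95% intervals cover less than 95%.

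The excess grows with each parameter fitted and each patient removed. It is therefore worst in the sex-specific and interaction analyses, which C8.p1 gives as the reason for the sample size. A chance difference between men and women, or an overly precise effect estimate, could be carried into the design of the next trial.

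**Working it through.** **Inputs from the document.** n = 24 analysed (12 per sex) or 26 randomised (13 per sex); two-sided alpha 0.05; classical sandwich; patient as cluster.

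**Assumptions not in the document.** Normal errors, complete end-of-period pairs and balanced sequences. The reference distribution is not stated, so both the normal and the t are shown.

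**Step 1: the plan's own power figures.** Table 7 gives no SD. An SD of within-patient differences of 4.41 points, solved from the 89% row, gives SE = 4.41/√24 = 0.90. A paired t test at a true 5% level (22 df) then has power 89%, 99.96% and 100% for differences of 3, 5 and 7 (table: 89%, 99%, 100%). Read as a test within one sex (n = 12, SE = 4.41/√12 = 1.27, 10 df), differences of 4, 5 and 7 give 81%, 94% and 99.8% (table: 80%, 94%, 100%). So Table 7 behaves like a test that is actually held at 5%.

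**Step 2: size of the planned test.** With complete pairs, the treatment effect comes from a regression of within-patient differences with p parameters. In a balanced two-period crossover, the uncorrected sandwich variance is (n − p)/n times the unbiased one. Hence

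actual size = 2 × P( t with n − p df > c × √((n − p)/n) ),

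with c = 1.96 for the normal reference, or the t(n − 2) quantile. Neither the SD nor the within-patient correlation enters. Example for n = 24, p = 2: 1.96 × √(22/24) = 1.877, and 2 × P(t with 22 df > 1.877) = 7.4%.

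| Model | n | p | Variance / true | Size, normal | Size, t(n − 2) |
|---|---|---|---|---|---|
| Treatment + period | 24 | 2 | 91.7% | 7.4% | 6.0% |
| + treatment × sex | 24 | 3 | 87.5% | 8.1% | 6.6% |
| + period × sex | 24 | 4 | 83.3% | 8.9% | 7.3% |
| Treatment + period | 26 | 2 | 92.3% | 7.2% | 5.9% |
| + treatment × sex | 26 | 3 | 88.5% | 7.8% | 6.5% |
| + period × sex | 26 | 4 | 84.6% | 8.5% | 7.1% |
| One sex, treatment + period | 12 | 2 | 83.3% | 10.4% | 6.9% |
| One sex, treatment + period | 13 | 2 | 84.6% | 9.9% | 6.8% |

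Coverage of a nominal 95% interval is one minus the size. Under the normal reference with 24 patients that is about 92.6% (p = 2) and 91.9% (p = 3), and about 90% within one sex.

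**Step 3: simulation.** Linear GEE with exchangeable correlation and no true effect (10,000-20,000 trials per model), n = 24, normal reference: 7.5% for treatment adjusted for period; with treatment × sex in the model, 8.5% for the DHEA effect and 8.2% for the interaction. A separate model with n = 12 gave 10.4%. The effect within one sex taken from a joint model gave 9.4%; across joint models, with and without period × sex, the range is 9.1-10.4% (7.7-8.8% with t(n − 2)). A standard GEE routine (2,000 trials) gave 7.9% at n = 24 and 10.3% at n = 12. With baseline as a third visit it gave 6.8% and 11.3%.

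**Step 4: towards the planned model.** Six one-df factors with all two- and three-way interactions need 1 + 6 + 15 + 20 = 42 parameters. There are 48-52 post-baseline MRI values, or 72-78 with baseline. Treatment × four covariates (assumed 50:50 subtype, 20:80 race, continuous age) gives 10-12.5% under the normal reference. Adding period × the same four gives about 15-18%. Much of that last rise comes from the number of terms.

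**Step 5: after correction, n = 24, t reference.** Kauermann-Carroll: 4.9% (treatment + period) and 4.9-5.0% (with treatment × sex). Mancl-DeRouen: 4.1% and 3.7-3.8%. A mixed-model-type t test: 4.9% (treatment + period).

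**The case against.** The strongest reply is that the figures are conditional and the consequence is small. The plan does not name a normal reference. With a t reference, the treatment-plus-period test is at most about one percentage point above 5%, and its standard error is only about 4-5% too small. The study is a pilot, claims no confirmatory error rate, and may proceed on a signal that is not significant. C8.o promises percentage and absolute changes and does not mention confidence intervals. The models computed here are also much smaller than the one described, whose larger fault is over-parameterisation.

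Much of this is fair, and it limits the severity. The reference distribution has to be stated beside every figure, and the 10% within one sex belongs to separate models or to a joint model with period × sex; without that term it is nearer 9%. That intervals will inform Phase II planning is an inference.

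The point itself survives. Every recomputed combination exceeds 5%, with either reference. Pilot status can justify omitting a multiplicity adjustment, but it does not make a standard error correct. Over-parameterisation adds to the inflation and does not excuse it.

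**Conclusion.** The concern holds. The plan names a specific variance estimator that does not hold its stated two-sided 5% level at this number of patients.

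- **Simple models, 24-26 patients:** 7.2-8.9% with a normal reference; 5.9-7.3% with an uncorrected t(n − 2).
- **Within one sex:** 9.9-10.4% from a separate model and 9.1-10.4% from a joint model with a normal reference; 6.8-6.9% and 7.7-8.8% with t(n − 2).

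These figures rest on normal errors, complete pairs and balanced sequences. The back-solved SD is used only to reproduce Table 7. The inflation is modest for the overall DHEA effect and larger where sex is examined. It should be fixed before analysis; it does not invalidate the trial.

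**What to change.** **Change.** For continuous end points, prespecify a reduced primary model: treatment, period, sequence, the stratification factors sex and PAH subtype, and treatment × sex for the sex hypothesis. Fit it in one of two ways, and name which:

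1. a linear mixed model with a patient random effect and Kenward-Roger degrees of freedom; or
2. GEE with a bias-corrected sandwich (Kauermann-Carroll or Mancl-DeRouen) and a t reference with degrees of freedom based on the number of patients, about 21-22 here.

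Use the second for non-continuous end points such as WHO functional class. Label all other two- and three-way interactions exploratory.

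**Cost.** One SAP paragraph and a software option; no new data. Against a normal-reference interval with the uncorrected variance, intervals widen by the ratio of critical values divided by √((n − p)/n). At n = 24 this is (2.074/1.96) × √(24/22) = 1.105 for treatment + period and (2.080/1.96) × √(24/21) = 1.134 with treatment × sex. That is about 10-13% for Kauermann-Carroll or the mixed model; Mancl-DeRouen costs 14-21% and is somewhat conservative. Within one sex at n = 12 the same arithmetic gives (2.228/1.96) × √(12/10) = 1.245, about 25%.

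**Order matters.** A correction does not rescue the large model. With treatment and period each crossed with four covariates, Mancl-DeRouen rejected in only about 1.3-2% of simulated trials and could not be computed in 34-40% of full-rank draws; 10-13% of draws were rank-deficient. The model must be reduced first.
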